For patients whose clinician pods are randomized to the intervention arm, the care team pod will receive an EPIC in-basket message indicating that the patient is eligible for Palliative Care and that a default referral order has been pended for that patient. Clinicians will be given an opportunity to respond if they do not want their patient to be referred to palliative care. For clinicians who do not respond, after the allotted time, the Clinical Research Coordinator will reach out to the patient to introduce palliative care and ask if ABBCI staff can schedule an appointment. For non-English speaking patients, an interpreter will assist research staff. For clinicians who respond no, the pended order will be removed and no patient contact by the research team will occur.

For eligible patients whose clinician pods have been randomized to the control arm, no intervention will be provided. Clinicians will refer patients to palliative care based on their usual practice.

Among patients in the intervention arm for whom palliative care referral is placed, who accept for a scheduler to call them to make an appointment, a trained research coordinator will approach 40

patients as a convenience sample to administer a baseline FACT-G survey (**Appendix A**). 40 randomly selected patients, matched on categories including age category and type of cancer, will be selected from the pods not receiving the intervention. For patients that choose to enroll in the survey component, a baseline FACT-G survey will be administered prior to discharge in-person via paper or electronically. Surveys will be repeated at 3, 6, 9, and 18-week intervals by either telephone or in-person at an in-person visit. For patients that complete the 9-week survey or any survey prior, a \$50 gift card will be given at the 9-week time point. Patients who miss their visits with palliative care will be contacted by the coordinator to identify why (**Appendix F**) and reschedule the appointment.

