## 9. Analysis plan

We will use REDcap, a HIPAA-compliant and secure database tool, to track all components of the study. Descriptive statistics will be used to estimate the frequencies, means, and standard deviations of the study variables. Differences between study groups in baseline characteristics and clinical outcomes will be assessed with the use of two-sided Fisher's exact tests and chi-square tests for categorical variables and independent-samples Student's t-tests for continuous variables. The unit of analysis will be the patient.

The primary study endpoint is a binary patient-level variable indicating completion of a palliative care visit within 24 weeks of the clinician behavioral nudge. This analysis will be conducted as a time-to-event analysis among all eligible advanced cancer patients. Cox proportional hazard regression analyses, adjusted for baseline covariates, will be used to examine the effect of nudges on completion of palliative care consultation for advanced cancer patients. Competing risk caused by patients who die within 24 weeks will be considered as censored in the analysis. Covariates will include patient and cancer-related variables. Patients will be followed for 24 weeks or until death. Using a longitudinal multilevel mixed-effects model with clustering by discharging clinician (intraclass correlation coefficient 0.5 based on prior randomized trial); a two-sided type I error rate of 0.05; and a baseline palliative care visit rate of 45% (standard deviation 10%), we expect that a sample size of 250 patients will give us 80% power to detect a meaningful 34 percentage point response in palliative care visits, considering the presence of a competing risk of 6-month mortality at 20%.

One secondary outcome will be (1) change in quality of life between 0 and 9 weeks (as measured by the Functional Assessment of Cancer Therapy – General (FACT-G) among patients who receive palliative care compared to matched controls. Multivariate linear regression analyses, adjusted for baseline scores, will be used to examine the effect of palliative care on completion of palliative care consultation for advance cancer patients. For intention-to-treat analyses, we will use the conservative method of carrying the most recent quality-of-life values forward to account for all missing data, including data that are missing owing to death.

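### FACT-G controls are matched on age category and cancer type, but the FACT-G regression names only the baseline score: adding the matching factors is a free, minor improvement

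*Combined protocol and SAP*

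**What the plan says.** **Selection (Section 8.2).** Among intervention-arm patients with a referral placed who agree to a scheduler's call, the coordinator approaches 40 "patients as a convenience sample to administer a baseline FACT-G survey". From the control pods the plan takes "40 randomly selected patients, matched on categories including age category and type of cancer". The word *including* leaves the list of factors open, and the plan does not say whether matching is by pair or by frequency.

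**Consent comes after selection.** The baseline survey is given "For patients that choose to enroll in the survey component". Sections 8.1 and 8.2 provide a decline form and a questionnaire for decliners, so refusals are expected. No replacement or re-matching rule is given.

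**Analysis (Section 9).** The contrast is "among patients who receive palliative care compared to matched controls". The model statement is "Multivariate linear regression analyses, adjusted for baseline scores, will be used", and no matching factor or matched-set term is named. By contrast, both Cox models are adjusted for baseline covariates, and for the primary one the plan adds: "Covariates will include patient and cancer-related variables".

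**Missing data (Section 9).** The intention-to-treat analyses use "carrying the most recent quality-of-life values forward to account for all missing data, including data that are missing owing to death".

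**The concern.** Age category and cancer type were thought important enough to match on, yet the model for the first-listed secondary outcome leaves them out. Two things follow.

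- **Precision.** A model that ignores a prognostic matching factor leaves its variation in the residual, although the design has already balanced it between groups. The reported standard error is then larger than it should be. With at most 40 patients per group, there is little precision to spare.
- **Balance.** Matching fixes the composition of the patients *selected*, not of those *analysed*. Patients can leave between the two steps by refusing the survey. Intervention patients can also leave if the contrast is run as defined, among those who receive palliative care: they are surveyed after accepting a call, not after a visit, and Section 8.2 foresees missed visits. If either loss depends on age or cancer type in one group and not the other, the model has no term to correct for it.

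**Working it through.** The plan gives no FACT-G effect size, SD, power, refusal rate or dropout rate, so there is no stated figure to reproduce. What follows uses labelled assumptions to find the order of magnitude.

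**Inputs from the plan:** 40 approached and 40 selected; adjustment for baseline score; last value carried forward. A two-sided 0.05 level and 80% power are stated for the primary outcome only and borrowed here for scale.

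**Assumptions:** one binary matching factor X, split 50/50. Within-stratum FACT-G SD is 1. The coefficient of week 9 on baseline is 0.5 and the residual variance is 0.75. X lowers the baseline score by g SD and the week-9 score by a further g SD given baseline, with g = 0.25, 0.5 or 1. The true group effect is zero. Clustering by pod is ignored.

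**1. Scale.** Detectable difference = (1.960 + 0.842) × √(2/n). At n = 40 per group this is 2.802 × 0.2236 = 0.63 SD, or 0.63 × √(1 − 0.25) = 0.54 SD with a baseline correlation of 0.5. At n = 28 (30% refusal) the figures are 0.75 and 0.65 SD.

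**2. Intact match: precision.** With X omitted, the residual variance is 0.75 + 0.25g²/(1 + 0.25g²). With X included, it is 0.75.

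- g = 0.25: 0.75 + 0.0154 = 0.765; SE ratio √(0.765/0.75) = 1.01.
- g = 0.5: 0.75 + 0.0588 = 0.809; SE ratio √(0.809/0.75) = 1.04.
- g = 1: 0.75 + 0.20 = 0.95; SE ratio √(0.95/0.75) = 1.13.

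A simulation of 3,000 runs per scenario agrees. Mean reported SEs are 0.201 without X and 0.194 with it at g = 0.5 (ratio 1.036), and 0.218 against 0.194 at g = 1 (ratio 1.12). Bias is 0.00 either way. Type I error without X is 4.8% at g = 0.5, which is indistinguishable from 5% (simulation error √(0.05 × 0.95/3000) = 0.4 points), and 2.6% at g = 1. The actual spread of the estimates hardly changes (0.196 with or without X at g = 0.5), so the gain is mainly in a correctly reported SE.

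**3. Refusal after selection.** If 30% refuse in each group, unrelated to X, bias is 0.00 with or without X. Now let control refusal be 15% in one stratum and 45% in the other. The heavily refusing stratum falls to 0.55/(0.55 + 0.85) = 39.3% of controls, against 50% of intervention patients, an imbalance of 0.107. The average within-group variance of X is (0.25 + 0.393 × 0.607)/2 = 0.244. With X omitted, bias = −g × 0.107/(1 + 0.244g²).

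| g | Formula | Simulated without X | Simulated with X |
|---|---|---|---|
| 0.25 | −0.026 | −0.030 | −0.005 |
| 0.5 | −0.050 | −0.054 | −0.005 |
| 1 | −0.086 | −0.085 | 0.000 |

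Simulation error is about 0.24/√3000 = 0.004. The sign would reverse if the losses fell in the other stratum.

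**4. Exclusion of non-receivers.** This was not simulated, but the arithmetic mirrors step 3. A 15%/45% loss in the intervention group moves the other stratum to 0.85/(0.85 + 0.55) = 61% against 50%, again an imbalance of 0.107.

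**5. Dropout after baseline.** With the same 15%/45% control loss (30% on average in each group) occurring after the baseline survey and values carried forward, the imbalance in X is 0.00. Bias is −0.02 SD with X and without it. Only a complete-case analysis, which the plan does not describe, would show −0.05 SD without X and 0.00 with it.

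**The case against.** **Adjustment for baseline alone is inferred from silence.** The plan excludes no covariate. The model sentence also goes on to name completion of a palliative care consultation as what is examined. That is fair. But the sentence sits in the FACT-G paragraph, and only FACT-G has baseline scores. The Cox models name baseline covariates and this model does not, so reading it as the FACT-G model with baseline adjustment is reasonable.

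**Matching already does the work.** A reader might infer that the matching is wasted or that the analysis is biased as it stands. The documents do not support that. The matching is used in choosing controls, and a linear model that omits the factors from an intact matched sample is unbiased and, at worst, conservative.

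**Deaths and dropouts.** A reader might also infer that each death or missed survey breaks a match. The plan's 20% six-month mortality implies 1 − 0.8^(9/26) = 7.4% dead by week 9 at a constant hazard, but that is not a share of matches lost. Carrying values forward keeps every patient with a baseline survey in the intention-to-treat analysis. Whether carrying forward is a good choice is a separate matter, and these covariates would not change it.

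**The bias is conditional and small.** It needs loss that differs between groups by a factor that predicts FACT-G beyond baseline, and no document figure shows this. Nor does the plan's wording require pair matching. This stands, and it limits the point to a minor one.

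**The precision gain could be partly spent.** Several age and cancer-type terms use degrees of freedom in a sample below 80. That is a reason to keep the categories few, not to leave the factors out.

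**Conclusion.** The point holds as a minor, nearly free improvement. The matching factors are not carried into the FACT-G model. With the match intact, the cost is a reported standard error about 4% too large at g = 0.5 (1% at 0.25, 12 to 13% at 1), with no bias. If refusal or non-receipt is unequal by a matching factor, bias of about 0.03 to 0.09 SD follows under the assumed 15%/45% split, against a detectable difference of 0.54 to 0.63 SD at 40 per group. Adjustment removes it. All these sizes rest on assumptions, since the plan gives no FACT-G variance, refusal rate or factor effect.

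A reader might take adjustment as curing the confounding in this contrast. It would not. Intervention patients are a convenience sample who had a referral placed and accepted a call, while controls are drawn at random within matching categories without that filter. Age and cancer type do not address that larger difference.

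**What to change.** In Section 9, specify the FACT-G model as a linear regression on group, baseline score and every matching factor, at least age category and grouped cancer type. Apply the same covariates to the 9-week score and the 18-week change.

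In Section 8.2, close the list of matching factors, say whether matching is by pair or by frequency, and state what happens when a selected patient refuses. In Section 9, state which patients the FACT-G intention-to-treat set contains, in particular whether intervention patients who never attend a palliative care visit stay in.

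**Cost:** a few degrees of freedom from at most about 80, kept low by using few, broad categories. Age and cancer type are already collected at baseline under Section 8.2, so no new data are needed for them. Naming the covariates now also prevents a choice made after the results are seen.

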### *3.2 Secondary outcomes*

- Change in quality of life between 0 and 9 weeks (as measured by the Functional Assessment of Cancer Therapy – General (FACT-G) among patients who receive palliative care compared to matched controls) (**Appendix A**)
- Quality of life at 9 weeks (as measured by the Functional Assessment of Cancer Therapy – General (FACT-G) among patients who receive palliative care compared to matched controls)

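### The FACT-G regression in Section 9 names the wrong dependent variable, and the 9-week score and 18-week change have no named model

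*Combined protocol and SAP*

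**What the plan says.** Section 3.2 of the combined protocol and SAP lists two secondary outcomes, both FACT-G: the change from 0 to 9 weeks and, as a separate bullet, "Quality of life at 9 weeks (as measured by the Functional Assessment of Cancer Therapy" instrument.

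Section 9 takes up the first: "One secondary outcome will be (1) change in quality of life between 0 and 9 weeks". The next sentence gives the method, "Multivariate linear regression analyses, adjusted for baseline scores", and its purpose: the model "will be used to examine the effect of palliative care on completion of palliative care consultation for advance cancer patients". The sentence after that carries earlier quality-of-life values forward where data are missing.

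Section 9 never names the 9-week score. It adds a change from 0 to 18 weeks as a further secondary outcome, without a model. A general rule stands at the start of the section: "Differences between study groups in baseline characteristics and clinical outcomes will be assessed", with "independent-samples Student's t-tests for continuous variables" and the patient as the unit of analysis.

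Section 8.2 defines who is surveyed. On the intervention side, 40 patients are approached as a convenience sample of those with a placed referral who accept a scheduler's call. On the control side, 40 are selected at random and matched on categories that include age and cancer type. Pods, not patients, are randomised.

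**The concern.** The impact on quality of life is a stated secondary objective, and FACT-G is the only measure among the secondary outcomes in Section 3.2. Yet no sentence in the plan makes FACT-G the dependent variable of a model. Followed to the letter, the one regression relates palliative care to whether a palliative care consultation took place. That is close to circular, fits a linear model to a yes/no event, and says nothing about FACT-G.

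The 9-week score and the 18-week change are then reached only by the general t-test rule, which does not use the baseline FACT-G that the trial collects. Baseline FACT-G is not named as a matching factor, and the two survey groups are assembled by different routes, so they may well differ at baseline. If one FACT-G result is adjusted and another is not, the two can disagree for reasons unrelated to palliative care, and the choice of which to emphasise is left open.

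**Working it through.** **1. The two sentences side by side.** The Cox sentence for the primary outcome says that the analysis "will be used to examine the effect of nudges on completion of palliative care consultation for advanced cancer patients". The FACT-G sentence says that it "will be used to examine the effect of palliative care on completion of palliative care consultation for advance cancer patients". Apart from the exposure (nudges in one, palliative care in the other) and one letter, the wording is the same. The likeliest explanation is that the ending was carried over.

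**2. Which FACT-G outcome has which analysis.**

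| Outcome | Listed in | Named model | Otherwise reached by |
|---|---|---|---|
| Change, 0 to 9 weeks | 3.2 and 9 | Linear regression adjusted for baseline, wrong dependent variable | General t-test rule |
| Score at 9 weeks | 3.2 only | None | General t-test rule |
| Change, 0 to 18 weeks | 9 only | None | General t-test rule |

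**3. Precision.** The plan gives no SD, effect size, power or correlation for FACT-G, so there is no figure of its own to reproduce. From the documents: 40 per group, taken as all analysed. Assumed: equal SD at both times, correlation r between baseline and follow-up, no clustering.

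- Unadjusted SE of the difference in scores = SD × √(2/40) = 0.224 SD.
- Adjusted SE = 0.224 × √(1 − r²) SD.
- Ratio, t-test on score to adjusted = 1/√(1 − r²).
- Ratio, t-test on change to adjusted = √(2(1 − r))/√(1 − r²) = √(2/(1 + r)).
- Detectable difference at two-sided 0.05 and 80% power = (1.96 + 0.84) × SE. For the t-test on the score this is 0.63 SD.

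| r (assumed) | Adjusted SE (SD) | SE ratio, t-test on score | SE ratio, t-test on change | Detectable difference, adjusted (SD) |
|---|---|---|---|---|
| 0.3 | 0.213 | 1.05 | 1.24 | 0.60 |
| 0.5 | 0.194 | 1.15 | 1.15 | 0.54 |
| 0.6 | 0.179 | 1.25 | 1.12 | 0.50 |
| 0.7 | 0.160 | 1.40 | 1.08 | 0.45 |

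**4. Baseline difference.** If the groups differ by d SD at baseline, an unadjusted comparison of scores is shifted by r × d and an unadjusted comparison of changes by (r − 1) × d.

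- d = 0.3 and r = 0.6 (assumed): 0.6 × 0.3 = +0.18 SD for the score; −0.4 × 0.3 = −0.12 SD for the change.
- d = 0.2 and r = 0.5 to 0.7 (assumed): +0.10 to +0.14 SD for the score; −0.10 to −0.06 SD for the change.

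The shifts have opposite signs, so an unadjusted score and an unadjusted change can point in different directions on the same data.

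**5. Change and score under adjustment.** Let Y0 and Y9 be baseline and 9-week FACT-G and G the survey group. If Y9 − Y0 = a + bG + cY0 + error, then Y9 = a + bG + (c + 1)Y0 + the same error. The group coefficient b and its SE are identical. A simulated data set with 40 per group gave 7.788 (SE 2.548) from both.

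**6. Pods.** With m surveyed patients per pod, the design effect is 1 + (m − 1) × ICC. The number of pods and an ICC for FACT-G are not given. For an assumed 4 pods per arm, m = 40/4 = 10; at an assumed ICC of 0.05 the design effect is 1 + 9 × 0.05 = 1.45. A nominal 5% patient-level test then has a true type I error of about 10%. Over 8 down to 2 pods per arm, the error is about 0.055 to 0.07 at ICC 0.01 and 0.07 to 0.16 at ICC 0.05. Adding baseline FACT-G alone would therefore not complete the model.

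**The case against.** The strongest reply is that this is a slip of wording with a recoverable meaning. The paragraph opens with FACT-G. The model is adjusted for baseline scores, which a consultation does not have. The next sentence deals with missing quality-of-life values. All of this stands: the intended model for the 0-to-9-week change is a baseline-adjusted regression of FACT-G. A reader might infer that the quality-of-life outcome has no valid analysis at all, or that the trial means to regress consultation on palliative care. The surrounding text does not support either.

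A reader might also infer that the plan commits the 9-week score to a t-test. It does not do so by name. The general rule follows the sentence on descriptive statistics, and read literally it also covers the change score and the binary primary endpoint, both of which have models of their own. It may be only a generic unadjusted layer. What stands is narrower: it is the only text that reaches the 9-week score and the 18-week change.

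Nor is a t-test invalid merely because it omits baseline. It is less precise and open to baseline imbalance. Ignoring pods, the matching and the non-random choice of intervention patients is the more serious weakness.

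Finally, listing both change and score at 9 weeks is redundant, not wrong, and the figures above rest on assumed correlations and imbalances. Both points are fair. They lower the grade of the problem, but an inferred intention is not a prespecified analysis.

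**Conclusion.** The sentence in Section 9 is wrong as written and should be corrected, and the 9-week score and 18-week change need a named model.

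The size is modest and illustrative. For the 9-week score, the t-test has an SE 15% to 40% larger than the adjusted analysis at correlations of 0.5 to 0.7. For a change score at the same correlations the loss is smaller, 15% down to 8%. An assumed baseline difference of 0.2 to 0.3 SD would move an unadjusted 9-week comparison by roughly 0.10 to 0.2 SD (0.2 × 0.5 = 0.10; 0.3 × 0.7 = 0.21). These figures assume 40 analysed per group, although 40 is the number to be approached on the intervention side and fewer may enrol, and the precision figures ignore clustering.

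This is a should-fix: a secondary outcome in about 80 patients with no stated power target, and the primary endpoint is untouched. Even the corrected model compares a convenience sample of patients who accepted a call with matched controls. Adjustment accounts for measured baseline FACT-G and the matching factors, not for that selection.

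**What to change.** In Section 9, replace the regression sentence with text to this effect: *FACT-G total score at 9 weeks is the dependent variable in a linear regression on survey group (intervention-arm survey patients versus matched controls), with baseline FACT-G and the matching factors as covariates and with allowance for clustering by pod. This model provides the result for both 9-week outcomes in Section 3.2, because change and score have the same group coefficient once baseline is included. The same model is used for FACT-G at 18 weeks. The general t-test rule does not apply to FACT-G outcomes.*

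Three details belong with it:

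- State how pods enter the model and, once their number is known, what small-sample correction is used.
- Define the groups by how they are sampled in Section 8.2. Sections 3.2 and 9 describe the comparison as patients who receive palliative care, whereas the survey sample is drawn from those who accept a scheduling call.
- Add one sentence stating that the comparison of accepters with matched controls remains open to selection after adjustment.

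The cost is a short paragraph in Section 9 and a cross-reference in Section 3.2. No new data are needed: baseline FACT-G, age, cancer type and pod are already recorded or known.

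### Carrying the last FACT-G value forward for all missing data, including after death, is not assured to be conservative, and the quality-of-life regression names the wrong outcome

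*Combined protocol and SAP*

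**What the plan says.** Section 9 defines one secondary outcome as the 0 to 9 week change in FACT-G, comparing patients who receive palliative care with matched controls. It plans a linear regression adjusted for baseline scores, but says that this regression "will be used to examine the effect of palliative care on completion of palliative care consultation for advance cancer patients". The next sentence gives the missing-data rule: "For intention-to-treat analyses, we will use the conservative method of carrying the most recent quality-of-life values forward", and continues, "to account for all missing data, including data that are missing owing to death". No reason is given for the label, and no missing-data sensitivity analysis or separate rule for death is stated. The opening of section 9 also plans t-tests for continuous variables. These could cover FACT-G but do not address missing data. The mixed-effects model mentioned in section 9 belongs to the power statement for the primary endpoint.

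Section 3.2 also lists "Quality of life at 9 weeks", and section 9 adds the change from 0 to 18 weeks. Section 8.2 schedules the follow-up after baseline: "Surveys will be repeated at 3, 6, 9, and 18-week intervals by either telephone or in-person"; section 8.1 gives the same weeks. On numbers, section 8.2 says that in the intervention arm "a trained research coordinator will approach 40" patients, with 40 matched patients selected from control pods. The only mortality figure is in the primary power statement, "considering the presence of a competing risk of 6-month mortality at 20" percent.

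**The concern.** Carrying a value forward assumes no change after the last survey. If scores decline, a patient who dies with only a baseline survey is scored as unchanged, which is better than a survivor who got worse. The effect on the group comparison depends on how scores move over time and on which group loses more data. The plan gives neither. A reader who trusts the label would take the reported difference as a floor on the true benefit, and that is not guaranteed.

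The wrong dependent variable is a separate drafting error. As written, no regression in section 9 names FACT-G as its response.

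**Working it through.** The plan gives no FACT-G standard deviation, effect size, decline or dropout rate, so it has no figure of its own to reproduce. Shifts below are palliative care minus control; negative is against palliative care.

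**1. Deaths by survey week.** Input: 20% six-month mortality (section 9). Assumption: constant hazard.
- 24-week base: 1 − 0.8^(9/24) = 0.080 (3.2 of 40) and 1 − 0.8^(18/24) = 0.154 (6.2 of 40).
- 26-week base: 1 − 0.8^(9/26) = 0.074 (3.0 of 40) and 1 − 0.8^(18/26) = 0.143 (5.7 of 40).

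**2. Shift from deaths alone.** Assumptions: hazard ratio 0.7 favouring palliative care, 5 to 15 points of decline not seen, 24-week base. Shift = −(gap in deaths) × (unseen decline).
- Week 9: gap 0.0803 − 0.0569 = 0.0234, so −0.12 to −0.35.
- Week 18: gap 0.1541 − 0.1105 = 0.0436, so −0.22 to −0.65.
- Against a simulated week 9 standard error of about 2.7, these are at most 0.35/2.7 = 0.13 and 0.65/2.7 = 0.24 standard errors. Week 18 itself was not simulated.

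**3. Shift from unequal loss of any cause, no true effect.** Assumptions: linear decline to week 9; last survey at week 0, 3 or 6 with equal chance. The unseen share of the decline averages (1 + 2/3 + 1/3)/3 = 2/3, so the size of the shift is decline × 2/3 × gap in missing share.
- Decline 10, gap 0.10: 0.67. Decline 10, gap 0.15: 1.0. Decline 15, gap 0.15: 1.5.
- The shift is toward the group with more missing data. If scores rise by 5 and the gap is 0.15, it reverses: 5 × 2/3 × 0.15 = 0.5.

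**4. Shift under a true effect.** Controls decline 10 and palliative care declines 2, so the true effect is 8.
- Missing 20%/20% (palliative care/control): 8 − 0.20 × 2/3 × 8 = 6.93.
- Missing 10%/25%: (−2 + 0.10 × 2/3 × 2) − (−10 + 0.25 × 2/3 × 10) = 6.47.
- Missing 25%/10%: (−2 + 0.25 × 2/3 × 2) − (−10 + 0.10 × 2/3 × 10) = 7.67.
- Fading benefit of 8, 5.5 and 3 points at weeks 3, 6 and 9, missing 20%/20%: 0.8 × 3 + 0.2 × (0 + 8 + 5.5)/3 = 3.3 against a true 3.0.

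**5. Simulation at week 9.** 6,000 runs, 40 per group, assumed SD 15 and within-patient correlation 0.6, missingness unrelated to scores. The mixed model used weeks 0, 3, 6 and 9 with unstructured covariance.

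| Scenario | Missing, palliative care/control | Carried forward | Mixed model |
|---|---|---|---|
| No effect, decline 10 | 20/20 | 0.01 (type I error 5.4%) | 0.03 |
| No effect, decline 10 | 10/25 | −0.92 (6.4%) | 0.09 |
| No effect, decline 10 | 25/10 | +1.02 (6.5%) | 0.03 |
| No effect, decline 15 | 10/25 | −1.54 (7.8%) | −0.06 |
| No effect, decline 15 | 25/10 | +1.49 (8.3%) | −0.02 |
| No effect, scores rise 5 | 10/25 | +0.43 | −0.06 |
| True effect 8 | 20/20 | 6.95 (power 73%) | 8.04 (74%) |
| True effect 8 | 10/25 | 6.47 (66%) | 8.00 (75%) |
| True effect 8 | 25/10 | 7.64 (81%) | 8.00 (75%) |

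With no effect and 10/25 missing, dropout driven by the last observed score gave −0.33 (decline 10) and −0.81 (decline 15) carried forward, against 0.03 for the mixed model in both. Dropout driven by the unseen next score gave −1.26 and −1.77 carried forward; the mixed model was also biased, by −0.65 in both.

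**The case against.** The best defence is that the label roughly fits what the documents suggest. Section 4 cites literature in which early palliative care improves survival, and section 8.2 says: "Patients who miss their visits with palliative care will be contacted by the coordinator to identify why". Both hint at fewer losses in the palliative care group, which works against palliative care if scores decline. These hints are weak. Section 4 is background, and survival is only exploratory in this trial. The recontact concerns missed visits, not missed surveys. Surveys can be done by telephone, and control patients can still be referred under usual practice.

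A second defence is size, and it stands. The part closest to the documents, deaths alone, is under 0.25 standard errors. Every larger figure rests on assumed dropout and trajectories. With equal 20% losses, type I error and power barely differ between the methods.

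A third is that the alternative has its own costs. It has a larger standard error, assumes data are missing at random, and implicitly extrapolates beyond death. This also stands, and is why death needs its own stated rule.

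Finally, the simulated type I errors and power treat patients as independent and ignore pod clustering and matching, so they are illustrative. The closed-form shifts in steps 2 to 4 concern mean differences and do not rest on independence.

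A reader might go further and infer that the rule favours palliative care. The documents do not support that: it needs, for example, more losses in the palliative care group with falling scores, and nothing in the plan points that way.

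**Conclusion.** The point holds in limited form. Calling the rule conservative is not assured, because its direction depends on the course of the scores and on which group loses more data. With equal losses, a null effect is unbiased, a growing benefit is understated, and a fading benefit can be slightly overstated. Where the rule does work against palliative care, it understates a growing benefit: a true 8 becomes about 6.5 to 7 at equal 20% losses or with more loss among controls. Null shifts of about 1 to 1.5 points need an assumed 15-point gap in missingness and a linear decline of 10 to 15 points.

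The text itself is clear on the rule, its extension to death, and the misnamed regression outcome. The magnitudes are less certain because most inputs are assumed. Only the FACT-G secondary outcomes are affected, in about 80 patients or fewer since 40 are only to be approached. The primary endpoint is not touched. The change should be made, but it is not critical to the trial's main conclusion.

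**What to change.** 1. Name FACT-G as the dependent variable of the quality-of-life regression.
2. Make the main analysis a baseline-adjusted repeated-measures mixed model of FACT-G at weeks 3, 6, 9 and 18. Use group, week, group-by-week, baseline and baseline-by-week as fixed effects, with unstructured within-patient covariance and an allowance for pod clustering. Read off the group difference at week 9, which serves both the change and the 9-week level because baseline is a covariate, and at week 18.
3. State how death enters the estimand. Add a rank-based composite placing death worst as a sensitivity analysis. Report missing surveys by group, week and reason, including patients with a baseline survey only.
4. Keep last value carried forward only as a sensitivity analysis and delete the word conservative.

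The cost is SAP wording and modest programming, with no new data. In simulation the mixed model's standard error was about 4% to 14% larger (2.78 against 2.67 at 8% missing in each group; at most 2.99 against 2.63). Patients with only a baseline survey contribute nothing to the recommended model, and the rank composite is harder to interpret. The change does not remove the difference in how the two survey groups are selected: a convenience sample of patients who accepted referral scheduling against matched controls.
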